7.5 Analysis of Primary Safety Endpoint

The primary adverse event (PAE) rate will be compared against a performance goal of 14% by testing the following hypotheses:

$$H_0: p_s \ge 0.14$$
 vs $H_A: p_s < 0.14$,

where p_s is the PAE rate (please refer to the study protocol for the definition of the primary safety endpoint). The mITT Analysis Set is the primary analysis set for the primary safety endpoint.

The primary analysis for the primary safety endpoint will be based on data from the Variable Flow study with borrowing from the mITT analysis set in the Main study, and will apply Bayesian methods and use a beta-binomial model.

The primary safety endpoint will be met if

$$\Pr(p_S < 0.14 | y, n) > 0.975$$

where p_s is the PAE rate. If the posterior probability of the safety rate being less than 14% is greater than 0.975 then the study will be considered to have demonstrated safety for the variable flow rate.

The following additional sensitivity analyses will be performed by updating the resulting posterior distribution for the safety endpoint for each stratum in the 2nd stage in Section 7.4 after accounting for missing data. Since the power term α_s controlling the borrowing does not depend on the missing outcome, the posterior distribution for the safety endpoint for each stratum is updated by incorporating the missing safety outcomes according to each scenario. Borrowing from the main study remains unchanged from the primary analysis, i.e., sensitivity analyses will be performed for missing primary endpoint data in the Variable Flow study.

• Tipping Point Analysis

Tipping point analysis will be performed for the primary safety endpoint in the mITT analysis set to assess the impact of missing outcomes in the Variable Flow study on the primary safety analysis. The posterior distribution will be updated each time to evaluate whether a tipping point is identified.

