Let $n_{s,Main}$ and $n_{s,Flow}$ be the number of subjects in the Main study and the Variable Flow study in the *s*-th stratum, respectively. For the Variable Flow study, subjects with missing outcomes will be excluded to obtain the following posterior distributions. The power term controlling the amount of information borrowed from the Main study for each stratum is obtained by $\alpha_s = \min\left(\frac{Nr_s/\Sigma r_s}{n_{s,Main}}, 1\right)$.

Let $y_{s,Flow}$ and $y_{s,Main}$ be the number of subjects with PAEs in the Variable Flow study and the Main study respectively in the *s*-th stratum. Assuming non-informative Beta(0.5, 0.5) prior for safety, the resulting posterior distribution for the safety endpoint for each stratum is Beta(0.5 + $Y_{s,borrow}$ + $y_{s,Flow}$, 0.5 + $NY_{s,borrow}$ + $(n_{s,Flow} - y_{s,Flow})$), where $Y_{s,borrow}$ = min ($\alpha_s \times y_{s,Main}, y_{s,Flow}$) and $NY_{s,borrow}$ = min ($\alpha_s \times (n_{s,Main} - y_{s,Main}), (n_{s,Flow} - y_{s,Flow})$).

Let $x_{s,Flow}$ and $x_{s,Main}$ be the number of subjects that are failure-free through 12 months in the Variable Flow study and the Main study respectively in the *s*-th stratum. Similarly, assuming non-informative Beta(1, 1) for the effectiveness endpoint, the resulting posterior distribution for the effectiveness endpoint for each stratum is Beta $(1 + X_{s,borrow} + x_{s,Flow}, 1 + NX_{s,borrow} + (n_{s,Flow} - x_{s,Flow}))$, where $X_{s,borrow} = \min (\alpha_s \times x_{s,Main}, x_{s,Flow})$ and $NX_{s,borrow} = \min (\alpha_s \times (n_{s,Main} - x_{s,Main}), (n_{s,Flow} - x_{s,Flow})))$. Only subjects with non-missing endpoint data in the main arm will be included for borrowing in the corresponding endpoint analyses. The posterior distributions of the primary endpoints are obtained by a weighted average of the posterior distributions across the 5 strata using equal weights.

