7.6 Analysis of Primary Effectiveness Endpoint

The primary effectiveness endpoint will be assessed by testing the following hypothesis:

$$H_0: p_E \le 0.50$$
 vs $H_A: p_E > 0.50$,

where p_E is the effectiveness success rate. The mITT Analysis Set is the primary analysis set for the primary effectiveness endpoint.

The primary analysis for the primary effectiveness endpoint will use complete follow-up data from the Variable Flow study with borrowing from the mITT analysis set in the Main study, and apply Bayesian testing using a beta-binomial model.

The primary effectiveness endpoint will be considered as success if

$$\Pr(p_E > 0.5 | x, n) > 0.975$$

where p_E is the 12-month effectiveness rate.

If the posterior probability of the effectiveness rate being greater than 50% is higher than 0.975, then the study will be considered to have demonstrated effectiveness of the device.

The Variable Flow study will be considered achieving study success when both the primary safety and primary effectiveness performance goals are met. The following additional

analyses will be performed at the time of the final effectiveness analysis. Similar to the safety sensitivity analyses, the posterior distribution for the effectiveness endpoint for each stratum is updated by incorporating the missing effectiveness outcomes according to each scenario. Borrowing from the main study remains unchanged from the primary analysis, i.e., sensitivity analyses will be performed for missing primary endpoint data in the Variable Flow study.

• Tipping Point Analysis

Tipping point analysis will be performed for the primary effectiveness endpoint in the mITT analysis set to assess the impact of missing outcomes in the Variable Flow study on the primary effectiveness analysis. The posterior distribution will be updated each time to evaluate whether a tipping point is identified.

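### The SAP's tipping-point analyses say borrowing stays unchanged, but the borrowed counts depend on the Variable Flow outcomes being imputed; read literally, the check can miss a tipping point

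*SAP*

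**What the plan says.** SAP 7.4 sets the power term α_s from the propensity scores and the number of Main subjects in the stratum. The counts actually borrowed are then capped, separately for events and non-events:

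- Safety: Y_borrow = min(α_s × y_Main, y_Flow) and NY_borrow = min(α_s × (n_Main − y_Main), n_Flow − y_Flow).
- Effectiveness: X_borrow and NX_borrow have the same form, for failure-free subjects and for failures.

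For the primary analysis of Variable Flow data, 7.4 states that "subjects with missing outcomes will be excluded to obtain the following posterior distributions".

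SAP 7.5 plans a tipping-point analysis that updates each stratum posterior with imputed outcomes. Its argument begins "Since the power term α_s controlling the borrowing does not depend on the missing outcome" and ends with the rule "Borrowing from the main study remains unchanged from the primary analysis". SAP 7.6 repeats the rule for effectiveness. Neither section says whether the min() terms are evaluated again.

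**The concern.** The stated reason does not support the rule. α_s is fixed, but the amount borrowed is not α_s alone, because each borrowed count is capped by a Variable Flow count. Imputing a missing subject as a PAE raises y_Flow in that stratum. If the cap was binding, 7.4 would then release more Main study PAEs into the posterior. With the borrowed counts frozen, the tipping-point posterior is not the one 7.4 gives for the same completed data.

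Protocol 18.9.8 leaves the Variable Flow sensitivity analyses to this SAP, and the tipping point is the only one listed for each primary endpoint. A gap at its adverse end could let a fragile result be described as robust.

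**Working it through.** **Inputs.** SAP 6: 92 Variable Flow subjects, up to 91 borrowed, PAE rate 7%, failure-free rate 65%, attrition 5% (safety) and 12% (effectiveness). SAP 7.4: five strata with equal weights, Beta(0.5, 0.5) prior for safety and Beta(1, 1) for effectiveness. SAP 7.5 and 7.6: goals of 14% and 50%, posterior threshold 0.975. Protocol Appendix D: 185 Main subjects.

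**Assumed, because the documents do not give them.** Equal similarity across strata (91/5 = 18.2 borrowed per stratum), 185/5 = 37 Main subjects per stratum before attrition, equal true rates in both studies, independent endpoints, and missingness unrelated to stratum.

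**The plan's own figure.** SAP 6 gives joint power close to 80%. Simulating 7.4 gives 0.78–0.79 without the caps and 0.83 with the caps as written (safety 0.87, effectiveness 0.95). The model is close enough to the plan's to use.

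**Direction.** Let m subjects be missing in a stratum, all set to PAE.

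1. y_Flow becomes y_Flow + m, and n_Flow − y_Flow does not move.
2. NY_borrow is therefore unchanged, so the second Beta parameter is the same under both rules.
3. min(α_s × y_Main, y_Flow + m) is at least min(α_s × y_Main, y_Flow), so the recomputed first parameter is equal or larger.
4. Hence Pr(p_S < 0.14) is never lower when frozen. The same argument applies to effectiveness failures.

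**How often the cap matters.** At the planning rates it binds on events in about 56% of strata for safety and on failures in about 62% for effectiveness. It binds in at least one stratum in over 98% of trials.

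**Worked safety example (assumed data).** Of 92 subjects, 87 are observed with PAEs of 1, 1, 1, 1, 0 by stratum, and one is missing per stratum. Main has 13 PAEs in 176: strata of 36, 35, 35, 35, 35 with 2, 2, 3, 3, 3 PAEs.

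- α_s = 18.2/36 = 0.506 in the first stratum and 18.2/35 = 0.52 in the others.
- α_s × y_Main = 1.01, 1.04, 1.56, 1.56, 1.56.
- Primary: borrowed PAEs are capped at 1, 1, 1, 1, 0, total 4.0. Posterior probability 0.9999.
- All five missing set to PAE, frozen: still 4.0 borrowed. Probability 0.993, a pass.
- Same data, recomputed: caps are 2, 2, 2, 2, 1, so 1.01 + 1.04 + 1.56 + 1.56 + 1.00 = 6.17 borrowed. Probability 0.974, a fail.

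Placing the 13 Main PAEs differently over the strata moved the recomputed value between 0.966 and 0.979. The opposite verdicts therefore occur for some data sets and not for others.

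**Simulation.** Share of trials passing the primary analysis that still pass with every missing outcome set adverse:

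| Endpoint and missingness | Who can be missing | Frozen | Recomputed | Difference |
|---|---|---|---|---|
| Safety, 5% | any subject | 59.4% | 45.6% | 13.7 points |
| Safety, 5% | event-free only | 60% | 47% | 13 points |
| Safety, 1.25% | event-free only | 93% | 90% | under 3 points |
| Effectiveness, 12% | any subject | 83.4% | 72.9% | 10.4 points |
| Effectiveness, 12% | event-free only | 84.7% | 77.9% | 6.8 points |

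Differences come from unrounded results. No trial reversed in any row. The effectiveness range is quoted as about 6–10%, rounded down at both ends.

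**Why 1.25% is included.** Protocol Appendix D (30.3.4) applies the same 5% and 12% to the Main study as dropout per year. Protocol 18.9.7 excludes a Variable Flow subject from the safety analysis only if PAE-free and missing the 3-month follow-up: 5% × 3/12 = 1.25%, or 92 × 0.0125 ≈ 1 subject, against 92 × 0.05 ≈ 5.

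**Mixed scenarios.** With k missing outcomes set adverse, the rest favourable and strata chosen at random, recomputing tips earlier, at the same point or later in 31%, 66% and 3% of trials for safety, and in 19%, 78% and 3% for effectiveness.

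**The case against.** The strongest reply is that the wording does not clearly freeze the borrowed counts. Apart from its last two words, the sentence in 7.6 runs "Borrowing from the main study remains unchanged from the primary analysis, i.e., sensitivity analyses will be performed for missing primary endpoint data in the Variable", and 7.5 has the same explanatory clause. It can be read as saying only that Main data are not varied. SAP 7.5 also presents the analysis as an update of the 7.4 stratum posterior, which contains the min() terms, so a programmer might re-evaluate them as a matter of course. On that reading nothing is overstated. This stands, and it limits the point to the literal reading. It does not remove the need for a change, because two programmers could code the sentence differently and report opposite robustness conclusions.

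A second reply is that freezing isolates the effect of missing data, whereas under recomputation one imputed PAE can release up to one more borrowed PAE. That could be a deliberate choice, but the SAP gives a different reason, and that reason does not lead to freezing.

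A reader might also infer that the rule always makes a tipping point rarer and later. The documents do not support that. The two rules agree unless a cap binds in a stratum with missing outcomes. When missing outcomes are set favourable, freezing withholds borrowed non-events and is conservative, which is how the 3% of reversals arise. Nor does the point touch trial success: SAP 7.6 and 9 rest it on the two primary posteriors alone, and the tipping point carries no decision rule.

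**Conclusion.** The concern holds in a limited form. SAP 7.5 justifies fixed borrowing by a property of α_s that the borrowed counts do not share. Taken literally, the tipping-point analyses are never less favourable than the SAP's own model when all missing outcomes are adverse. At the planning rates they would miss a tipping point in about 13–14% of passing trials for safety at 5% missing, under 3% at 1.25% missing, and about 6–10% for effectiveness at 12% missing.

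The sizes depend on the assumptions listed above, especially how missingness arises and the Main study rate. For safety at 5% missing, a Main PAE rate of 4% gives 67% frozen against 61% recomputed still passing, and a rate of 10% gives 54% against 35%. The direction at the all-adverse end follows from the formulas and does not depend on the simulation. Only the robustness statement is at stake.

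**What to change.** In SAP 7.5 and 7.6, replace the sentence on unchanged borrowing with: *Main study outcomes and α_s remain fixed and only missing Variable Flow outcomes are imputed; the borrowed counts (the min() terms of Section 7.4) are recomputed for each imputed scenario.* This keeps the limit to Variable Flow outcomes, which simply deleting the sentence would lose.

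Also state how imputed outcomes are allocated: each missing subject stays in their own propensity stratum, and the worst-case allocation of a given number of adverse outcomes is reported.

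The cost is a short text change in two sections and a small programming change, with no new data and no change to the primary test. The downside is that the robustness statement may be less favourable.

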7.6 Analysis of Primary Effectiveness Endpoint

The primary effectiveness endpoint will be assessed by testing the following hypothesis:

$$H_0: p_E \le 0.50$$
 vs $H_A: p_E > 0.50$,

where p_E is the effectiveness success rate. The mITT Analysis Set is the primary analysis set for the primary effectiveness endpoint.

The primary analysis for the primary effectiveness endpoint will use complete follow-up data from the Variable Flow study with borrowing from the mITT analysis set in the Main study, and apply Bayesian testing using a beta-binomial model.

The primary effectiveness endpoint will be considered as success if

$$\Pr(p_E > 0.5 | x, n) > 0.975$$

where p_E is the 12-month effectiveness rate.

If the posterior probability of the effectiveness rate being greater than 50% is higher than 0.975, then the study will be considered to have demonstrated effectiveness of the device.

The Variable Flow study will be considered achieving study success when both the primary safety and primary effectiveness performance goals are met. The following additional

analyses will be performed at the time of the final effectiveness analysis. Similar to the safety sensitivity analyses, the posterior distribution for the effectiveness endpoint for each stratum is updated by incorporating the missing effectiveness outcomes according to each scenario. Borrowing from the main study remains unchanged from the primary analysis, i.e., sensitivity analyses will be performed for missing primary endpoint data in the Variable Flow study.

• Tipping Point Analysis

Tipping point analysis will be performed for the primary effectiveness endpoint in the mITT analysis set to assess the impact of missing outcomes in the Variable Flow study on the primary effectiveness analysis. The posterior distribution will be updated each time to evaluate whether a tipping point is identified.

7.7 Analysis of Secondary Endpoints

No formal statistical hypothesis and inferential statistics will be formulated and performed for the secondary endpoints. Descriptive statistics will be provided on all secondary safety endpoints in the Safety analysis set in the Variable Flow study. Similarly, the secondary Effectiveness endpoints will be summarized descriptively in the PP analysis set in the Variable Flow study. The following analyses will be completed when all subjects complete their 12-month follow-up.

7.7.1 Analysis of Secondary Safety Endpoint

The following analyses for the secondary safety endpoints will be conducted in the Safety analysis set in the Variable Flow study.

- Incidence of Unanticipated Adverse Device Effects (UADEs) will be summarized descriptively.
- Incidence of Serious Adverse Events (SAEs) within 7 days (early onset), >7 to 30 days (peri-procedural) and >30 days (late onset) will be summarized descriptively by three timeframes.
- Incidence of bleeding complication (ISTH definitions): major, clinically relevant nonmajor and minor bleeding

The ISTH (International Society on Thrombosis and Haemostasis) recommended the following criteria for defining different severity levels of bleeding complications of the atrial fibrillation and non-surgical venous thromboembolism cases ¹,

 Major bleeding: having a symptomatic presentation and 1) Fatal bleeding, and/or 2) Bleeding in a critical area or organ, such as intracranial, intraspinal, intraocular, retroperitoneal, intra-articular or pericardial, or intramuscular with compartment syndrome, and/or 3) Bleeding causing a fall in hemoglobin level of 20 g L-1 (1.24 mmol L-1) or more, or leading to transfusion of 2 or more units of whole blood or red cells Clinically relevant non-major bleeding: Any sign or symptom of hemorrhage (e.g., more bleeding than would be expected for a clinical circumstance, including bleeding found by imaging alone) that does not fit the criteria for the ISTH definition of major bleeding but does meet at least 1 of the following criteria: 1) requiring medical intervention by a healthcare professional, 2) leading to hospitalization or increased level of care, 3) prompting a face-to-face (i.e., not just a telephone or electronic communication) evaluation

All bleeding complications after the index procedure will be included in this analysis. The number of bleeding complications, number of subjects with bleeding complications, percentage of subjects with bleeding complications, rate of ISTHdefined major bleeding complications (per person-month) will be presented overall and by ISTH-defined categories (i.e. major, clinically relevant non-major, and minor).

7.7.2 Analysis of Secondary Effectiveness Endpoint

Descriptive statistics will be provided on the following endpoints in the PP analysis set in the Variable Flow study.

• Acute Procedural Success: confirmation of entrance block in all PVs.

The number and percentage of subjects with acute procedural success and the corresponding 97.5% exact binomial lower confidence bound will be presented.

• PV Isolation/ Acute Reconnection/ Touch-Up Application:

• PV isolation at the end of the procedure

Percent of subjects and percent of targeted PVs where PVI was achieved at the end of the index procedure, including additional RF application for the PV reconnection if applicable, will be summarized descriptively.

The achievement of PVI at the end of the procedure will be identified at the following time points, including 1) before the required 20-min waiting period, or 2) after the adenosine challenge was performed, and 3) after additional RF application for PV reconnection, whichever occurs last during the index procedure.

• Rate of PVI achieved at the end of procedure among targeted veins:

= number of targeted veins reaching PVI at the end of procedure total number of targeted veins

• Rate of PVI achieved at the end of procedure among subject:

= number of subjects reaching PVI at the end of procedure total number of subjects undergone ablation procedure

• PV isolation using QMODE+ as only ablation strategy

Percent of subjects and percent of targeted PVs where PVI was achieved at the end of the index procedure by using only the QMODE+ during the procedure will be summarized descriptively.

• Rate of PVI achieved by using QMODE+ only among targeted veins:

= number of targeted veins reaching PVI at the end of procedure by using QMODE + only total number of targeted veins

• Rate of PVI achieved by using QMODE+ only among subjects:

= $\frac{number \ of \ subjects \ reaching \ PVI \ at the \ end \ of \ procedure \ by \ using \ QMODE \ + \ only}{total \ number \ of \ subjects \ who \ underwentablation \ procedure}$

• PVs isolation after first encirclement (evaluated prior to the 20-minute waiting period and adenosine challenge)

Percent of subjects and percent of targeted PVs where PVI was achieved before the required 20-min waiting period, regardless the additional application was applied to remove the PV reconnection or not, will be summarized descriptively.

• Rate of PVI achieved prior to 20-min waiting period among targeted veins:

= number of targeted veins reaching PVI prior to 20 – min waiting period total number of targeted veins

• Rate of PVI achieved prior to 20-min waiting period among subjects:

number of subjects reaching PVI prior to 20 – min waiting period total number of subjects who underwent ablation procedure

• PV isolation after first encirclement without acute reconnection (evaluated after waiting period and adenosine challenge)

Percent of subjects and percent of targeted PVs where PVI was achieved after the adenosine challenge and with no additional RF applications to remove PV reconnection will be summarized descriptively.

• Rate of PVI achieved after adenosine challenge among targeted veins:

 $number\ of\ targeted\ veins\ reaching\ PVI\ after\ adnosine\ challenge\ and\ without\ acute\ reconnection$

• Rate of PVI achieved after adenosine challenge among subject:

= number of subjects reaching PVI after adenosine challenge and without acute reconnection total number of subjects who underwentblation procedure

o Acute PV reconnection after first encirclement

Percent of subjects and percent of targeted PVs where PV reconnection was observed after the adenosine challenge will be summarized descriptively.

• Rate of acute PV reconnection among targeted veins:

= number of targeted veins with PV reconnection after adenosine challenge total number of targeted veins

Rate of acute PV reconnection among subject:

= number of subjects with PV reconnection after adenosine challenge total number of subjects who underwent ablation procedure

• PVs with touch-up (i.e. touch-up or ablation for acute reconnection)

Percent of subjects and percent of targeted PVs where additional RF applications was applied to remove PV reconnection, regardless the timing of PVI or the confirmation of the entrance block, will be summarized descriptively.

Rate of PV touch-up among targeted veins:

 $= \frac{number of targeted veins with touch - up RF application}{total number of subjects who underwent ablation procedure}$

• Rate of PV touch-up among subjects:

 $= \frac{number of subjects with touch - up RF application}{total number of subjects who underwent ablation procedure}$

• Repeat ablation procedures during 12-month period post procedure

• Rate of repeat procedures

All repeat ablation procedures after the index procedure will be summarized. The number of repeat procedure, number of subjects undergoing repeat procedure, percentage of subjects undergoing repeat procedure will be presented overall and by timing of the repeat procedure (i.e. during blanking period (Day 1-90), and during the evaluation period (Day 91-365)) and by type of arrhythmia being treated (e.g. AF, AFL, atypical flutter, etc.).

= number of subjects undergoing repeat ablation for study arrhythmia total number of subjects who underwent the index ablation procedure

Additionally, Kaplan-Meier analysis will also be performed to characterize the time to first repeat procedure post the index procedure.

• PV re-isolated among all the targeted PVs at repeat procedure

Percent of PVs that were targeted for ablation at both the index and repeat procedure and reached isolation in the repeat procedure will be presented overall and by timing of the repeat procedure (i.e. during blanking period (Day 1-90), and during the evaluation period (Day 91-365)) and by type of arrhythmia being treated (e.g. AF, AFL, atypical flutter, etc.).

= number of PV reisolated at repeat procedure total number of PVs being targted at index and repeat procedures

• Requiring additional lesions for non-PV triggers among the repeat ablation procedures

Percent of repeat ablation procedures requiring new linear lesions/ foci lesion which were not ablated in the index procedure will be will be presented overall and by timing of the repeat procedure (i.e. during blanking period (Day 1-90), and during the evaluation period (Day 91-365)) and by type of arrhythmia being treated (e.g. AF, AFL, atypical flutter, etc.).

= number of repeat procedure requiring new linear (foci)lesion not previsouly ablated in the index procedure total number of repeat procedures

• 12-Month Single Procedure Success

 12-month Single Procedure Success is defined as freedom from documented AF/AFL/AT recurrence (episodes ≥ 30 secs) during the evaluation period after a single ablation procedure and off AADs. Any repeat ablation procedure or AAD therapy will be deemed effectiveness failure for this analysis.

The 12-month single procedure success rate will be summarized descriptively. Kaplan-Meier analysis will be performed to characterize the time to the first single procedure failures post the index procedure.

